6.10 Agent Destruction/Disposal

At the completion of investigation and after submission of the site final close out visit report by the CPN Compliance Coordinator, all unused study agent will be destroyed on site according to institutional SOPs.

7. CLINICAL EVALUATIONS AND PROCEDURES
7.1 Schedule of Events

Parts I and II													
Study Visit	Pre-Registration	Screening/ Baseline ¹	Registration/ Randomization Week 0 ²	Week 2	Week 4 (+/- 7 days)	Week 6 (+/- 7 days)	Week 10	Week 12	Weeks 16, 28, and 40 (+/- 7 days)	Week 52	Week 53 Booster	Week 55	Week 57 (+/- 7 days)
Informed Consent	X												
History and Physical		X								X			
Vital Signs		X		X			X			X		X	
Baseline Symptoms		X											
Concomitant Medications		X		X	X	X	X	X	X	X	X	X	X
CBC w/5-part diff., platelets		X		X			X			X		X	
Blood chemistry panel (potassium, sodium, chloride, bicarbonate, creatinine, serum glucose, BUN, total bilirubin, alk phos, and uric acid)		X								X			
Antinuclear antibody (ANA)		X								X			
AST/SGOT; ALT/SGPT		X		X			X	X		X		X	
Research blood ³		X ³		X ³			X ³	X ³		X ³		X ³	
Obtain medical record release, if applicable		X											

Study Visit	Pre-Registration	Screening/ Baseline ¹	Registration/ Randomization Week 0 ²	Week 2	Week 4 (+/- 7 days)	Week 6 (+/- 7 days)	Week 10	Week 12	Weeks 16, 28, and 40 (+/- 7 days)	Week 52	Week 53 Booster	Week 55	Week 57 (+/- 7 days)
Obtain colonoscopy reports and specimens ^{4,5}		X											
Pregnancy test ⁶		X	X	X			X				X		
Vaccination (MUC1/POLY-ICLC or placebo)			X	X ⁷			X ⁸				X ⁹		
Adverse Events			X	X	X	X	X	X	X	X	X	X	X
Phone call					X	X			X				X
QOL Questionnaire(s)			X ¹¹								X ¹¹	X ¹¹	

Part III		
Study Visit/Event	Weeks 88, 104, 130 (+/- 10 days)	Week 156 (Year 3) ¹²
Update medical/surgical history		X
Phone call	X ¹⁰	
Concomitant medications	X	X
Research blood ³		X ³
Obtain medical record release, if applicable		X
Obtain colonoscopy reports and specimens		X
QOL Questionnaire		X ¹¹

1. Baseline evaluations must occur after pre-registration and must be completed ≤ 28 days prior to registration/randomization.
2. Week 0 injection must be administered ≤ 14 days after registration/randomization. The date on which the injection is administered will become the “zero” time point from which all subsequent time points will be measured.
3. Research blood (blood for immunology assays and other endpoints) must be collected M-Th only and shipped overnight for next day analysis.
4. Operative notes, endoscopy reports, and/or pathology reports must be reviewed locally to confirm that the candidate meets at least one of the entry criteria specified in inclusion criterion 4.1.1.1. Participants will need to registered/randomized within 1 year from the initial polyp removal, unless evidence of an advanced adenoma is identified at the subsequent colonoscopy, in which case the timing for eligibility will start anew. Note: if

- participants are scheduled for early repeat colonoscopy, such as within 12 months of the colonoscopy that identified the advanced adenoma, to insure complete removal of the qualifying lesion, they should be enrolled after that repeat colonoscopy insures that no residual adenoma is present.
5. Endoscopy report and/or pathology report confirming qualifying advanced adenoma diagnosis as well as the fact that all polyps and adenomas have been removed must be submitted by FAX or email to the CPN Quality Assurance Specialist (QAS) within 30 days after registration/randomization.
 6. Pregnancy test (serum or urine) will be performed for female participants of childbearing potential at baseline/screening and prior to each injection (Week 0, 2, 10, and booster vaccine). Week 0 pregnancy test does not have to be repeated if ≤ 7 days since baseline/screening test. Should a woman become pregnant or suspect she is pregnant while participating in this study, she should inform her study physician immediately.
 7. Week 2 injection may not occur less than 14 days after Week 0 injection. It may occur up to 28 days after the Week 0 injection.
 8. Week 10 injection should occur 7-10 weeks (ideally 8 weeks) after Week 2 injection.
 9. Week 53 booster should ideally occur as soon as possible after the week 52 monitoring test results are available. It may occur up to 4 weeks after the Week 52 visit.
 10. Telephone contact will be made to monitor concomitant medications, possible adenoma recurrence, and the timing of follow up surveillance colonoscopy.
 11. The Risk, Regret, and Symptom Questionnaire (Appendix D) will be administered before the Week 0 injection, after the Week 53 injection, and at the Week 156 visit. The Was It Worth It (WIWI) Questionnaire (Appendix C) will be administered during the Week 55 visit.
 12. The timing of the follow up surveillance colonoscopy will vary among individuals and institutions. Ideally, the participants will return at Week 156 (+/- 4 weeks) to update their medical/surgical history, concomitant medications, and immune response. If any clinical surveillance colonoscopies are scheduled between Weeks 52 and 156, it would be ideal to gather the updated med/surg history and concomitant medications within 2 weeks before the scheduled colonoscopies. If this is not possible, it will not be considered a protocol deviation. These data should still be gathered and the timing noted. Reports and specimens from the colonoscopy should be gathered within 30 days after the colonoscopy. Colonoscopy and pathology reports must be submitted by FAX or email to the CPN Quality Assurance Specialist (QAS) within 30 days after the date of the procedure.

Summary of Parameters for Visit Timing

Week/Visit	Window	Ideal timing
0	Within 28 days of screening visit	within 1 week
2	No earlier than 2 weeks and up to 4 weeks from week 0 injection	2 weeks from week 0 injection
10	7 – 10 weeks from week 2 injection	8 weeks from week 2 injection
12	10 – 21 days after week 10 injection	2 weeks from week 10 injection
52	51 to 54 weeks from week 0 injection	52 weeks
53	As soon as possible after week 52 monitoring tests return	Within 4 weeks of week 52 visit
55	10 – 21 days from week 53 injection	2 weeks
156	Within 4 weeks of any planned colonoscopy	2 weeks before colonoscopy

Note: If the visit/event takes place within the window specified above, it will not be considered a deviation. However, for consistency, every effort should be made to schedule visits and events according to the “ideal timing” column. The scheduling of subsequent injections should be based on timing of previous injection. If sampling or injections are delayed, they should still occur (even after colonoscopy for week 156 titer, for example), and timing should be noted.

7.2 Baseline Testing/Prestudy Evaluation

After participants have been informed about the study and have signed the informed consent document, they will be pre-registered and assigned a unique participant identification number (PID). They will then undergo initial screening tests and procedures. The order in which these tests and procedures is conducted is flexible within the designated study timelines and should be consistent with good clinical practice and institutional policies and procedures. These tests and procedures include a physical exam, documentation of medical/surgical history, documentation of any existing baseline symptoms, allergies, and concomitant medications, and baseline blood tests. Baseline blood tests include CBC with 5-part differential, potassium, sodium, chloride, bicarbonate, creatinine, serum glucose, BUN, total bilirubin, alkaline phosphatase, uric acid, AST/SGOT, ALT/SGPT, and antinuclear antibody (ANA). Blood will also be drawn at baseline for the immune assay (IgG assay). Authorization to obtain data and specimens from the clinical colonoscopies will be obtained.

If participants are eligible and willing to participate, they will be registered to the study and randomized to one of two intervention arms (vaccine versus placebo/saline injection). Values of the stratification factors will be recorded and the CPN electronic-based randomization system will be utilized to ensure that randomization of participants to appropriate study arms, while balancing the stratification variables, is carried out successfully.

7.3 Evaluation During Study Intervention

Vaccine or placebo/saline will be administered at weeks 0, 2, and 10, with a booster at week 53. Females of childbearing potential will be required to document negative pregnancy test prior to each injection. Immune response will be tested 2, 10, 12, 52, 55, and 156 (Year 3). Adverse events will be evaluated at regular time points after each injection (See Section 11.1 for details).

At the Week 2 and Week 12 visits, if any erythema or induration injection site reactions are still present, the participant's measurement of the diameter will be compared with the study team's measurement for the purpose of validating the participant-reported measurement.

Blood tests to monitor toxicity will be conducted at weeks 2, 10, 12, 52, and 55. At weeks 2, 10, and 55, CBC with 5-part differential, AST/SGOT, and ALT/SGPT will be performed. At week 12, AST/SGOT and ALT/SGPT will be performed. Possible adverse events and concomitant medication information will be captured at each visit and by telephone at weeks 4, 6, 16, 28, and 40. All visits will involve informing the participant of the results of previous blood tests.

Participants will undergo an evaluation at week 52, including a physical exam, blood tests for immune response and toxicity monitoring, discussions of the results of previous tests, discussions of possible adverse events and concomitant medications. The following blood tests will be performed: CBC with 5-part differential, potassium, sodium, chloride, bicarbonate, creatinine, serum glucose, BUN, total bilirubin, alkaline phosphatase, uric acid, AST/SGOT, ALT/SGPT, and antinuclear antibody (ANA).

Risk, Regret, and Symptom Questionnaires will be administered prior to the Week 0 injection and at weeks 53 and 156. The Was It Worth It (WIWI) Questionnaire will be completed at Week 55.

7.4 Evaluation at Completion of Study Intervention

The final blood tests for immune response and toxicity monitoring will take place at Week 55. Those results will be provided, and discussions of adverse events and concomitant medications will take place at Week 57 by telephone,

7.5 Post-intervention Follow-up Period

For the purpose of monitoring adenoma recurrence and concomitant medications, contact by telephone will be made approximately every six months until Week 156 (Year 3) or the time of reported adenoma recurrence. Reports and specimens from any clinical colonoscopies will be obtained. Immune response will be tested. See Section 7.1 for details.

7.6 Methods for Clinical Procedures

7.6.1 Vaccine injection procedure details
See Section 5.2.

7.6.2 Colonoscopy data and specimens
Data will be abstracted from operative and pathology reports from clinical surveillance colonoscopies to confirm initial eligibility (Section 4.1.1.1) and to document any recurrence or new diagnosis. Permission will be obtained, if applicable, from each participant to obtain paraffin blocks and/or unstained slides from any specimens removed during the clinical surveillance colonoscopies.

8. CRITERIA FOR EVALUATION AND ENDPOINT DEFINITION

8.1 Primary Endpoint

The primary endpoint for this study is to compare the ratio of the week 12 to week 0 IgG levels between the MUC1 vaccine and placebo. It is hypothesized that this ratio will be increased in patients treated with the MUC1 vaccine as compared to patients receiving the placebo. All randomized participants who are evaluated at week 0 and week 12 and have IgG values from those time points will be evaluable for the primary endpoint of this study using a modified intent-to-treat principle. If we are missing the data for Week 0 or Week 12, we will be missing data for the analysis since the primary endpoint will compare the ratio of the Week 12 to Week 0 IgG levels between the MUC1 vaccine and the placebo.

The measurement of vaccine-induced anti-MUC1 IgG will be determined by Enzyme-Linked Immunosorbent Assay (ELISA). See Section 10.2.2.

8.2 Secondary and Translational Endpoints

The secondary endpoints will include the following:

- The Part I key secondary endpoint will be a comparison of the proportion of patients with at least a 2-fold increase in the IgG ratio between the 2 arms at 12 weeks.

- The Part II key secondary endpoint will assess the booster response at week 55 vs. week 52 for the vaccine as compared to placebo.
- The Part III key secondary endpoint will compare the adenoma recurrence rate from surveillance exams occurring at least one year and up to three years after Week 0 vaccine administration – MUC1 peptide versus placebo.

In addition to these key powered endpoints for the 3 different parts, we will also assess the following additional secondary endpoints:

- Comparison of adverse events between the MUC1 vaccine and placebo during Part 1 and 2.
- Comparison of the adenoma recurrence rates between MUC1 and placebo by excluding the following types of adenomas. These adenomas are excluded since they may represent missed or residual adenomas from the baseline exam. These analyses are exploratory.
 - Participants with adenomas ≤ 5 mm,
 - Participants with adenomatous tissue which may represent residual adenoma at the site of the previous advanced adenoma,
 - Participants with adenomatous tissue detected in the same segment of the bowel as the previous advanced adenoma.
- Assessment of participant-reported injection site reaction events from the Vaccine Report Card.

In addition, we will assess the following translational endpoints:

- To compare the anti-MUC1 antibody titer at the time of surveillance colonoscopy for the purpose of evaluating the anti-MUC1 antibody response in relation to adenoma recurrence. Since surveillance colonoscopy is generally at 3 years after an advanced adenoma, this titer will typically be obtained at approximately week 156.
- To evaluate MUC1 expression on baseline advanced adenomas and on recurrent adenomas detected at surveillance colonoscopy. Based on current knowledge of MUC1 expression and function in tumor cells, MUC1 negative adenomas are not expected to grow as immune escape variants, but this has never been tested before and the trial will provide an appropriate setting to study this issue.
- To evaluate levels of circulating myeloid derived suppressor cells (MDSC) in the vaccinated and the placebo group and correlate with anti-MUC1 antibody levels and adenoma recurrence (See Section 10.2.2).
- To establish a biospecimen repository archive including live cells, plasma, and germline DNA for future immunologic and other assays, for testing not currently accommodated within the budget of this trial.

Where appropriate, secondary and translational analyses will be based on all randomized participants (i.e. adverse event analyses) or defined participant subgroups.

8.3 Off-Agent Criteria

Participants may stop taking the study agent due to: completion of the planned intervention period, development of an adverse event or serious adverse event, inadequate agent supply, noncompliance, use of concomitant medications, medical contraindication, refusal, ineligibility (see Section 8.4), major

treatment violation (see Section 8.4) or alternative treatment. Participants will continue to be followed, if possible, for safety according to the intended schedule of events (see Section 7).

Participants discontinuing the planned intervention prematurely will be encouraged to complete the Post-Intervention Evaluation tests and procedures as appropriate (if participant does not refuse, is not lost to follow-up, or unless it is clinically contraindicated). See Section 8.4 for further details as to data submission for participants deemed Ineligible after starting treatment or classified as a Major Treatment Violation (i.e., protocol requirements regarding intervention during the first week post-randomization were severely violated). In such cases, all data and all on-study materials, collected up until the point of confirmation of ineligibility or major violation status must be submitted.

8.4 Off-Study Criteria

Participants may go “Off-Study” for the following reasons: development of an adverse event or serious adverse event, death, lost to follow-up, participant withdrawal, physician decision, protocol violation, completion of study, or other (with detailed comments provided). Reason(s) will be noted in the participant’s research records, with the primary reason clearly identified. The participant will be classified as (Off Study/Off Agent). Data submission and follow-up after participants are determined to be a screen failure or “Off-Study/Off-Agent” for specific situations is noted below:

Ineligible: A registered participant is deemed ineligible if the participant does not satisfy each and every eligibility criterion for study entry.

- If participants received study intervention, on-study materials and all data up until the point of confirmation of ineligibility will be submitted.
- If participants did not receive study intervention, on-study materials must be submitted. No further data submission is necessary. No follow-up is required.

Major Treatment Violation: A registered participant is deemed as being in major treatment violation by the coordinating center, if the participant’s very first treatment/intervention administration is so grossly administered in error, that the participant’s data can no longer be used for the primary endpoint. These cases are typically rare.

- On-study material and all data up until the point of confirmation of a major violation must be submitted.

Cancel: A registered participant is deemed a cancel if he/she refuses the study before any study intervention is given.

- On-study material must be submitted. No further data submission is necessary. No follow-up is required.

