6.2 Reported Adverse Events and Potential Risks

The side effects listed in the table below are based on a variety of previous studies that were similar to this study in some ways but different in important ways (including stronger doses) that may have led to different side effects. In the previous study that was most similar to this study, no autoimmune disease or serious side effects were identified.

Possible Side Effects of the MUC1 – poly-ICLC vaccine:

Common, Some May Be Serious In 100 people who receive the injection, more than 20 may have:

• Redness at injection site (erythema)• Pain/soreness at injection site• Flu-like symptoms, which may include fever chills, headache, fatigue, muscle pain, and joint pain• Night sweats• Loss of appetite• Low albumin blood test result (a type of protein in the blood)

The redness and soreness generally resolve within a few days to a week. Generally, acetaminophen (Tylenol®) is sufficient for pain relief. The flu-like symptoms generally resolve within 12-24 hours. Acetaminophen (Tylenol®) generally helps with these symptoms if they occur.

Occasional, Some May Be Serious In 100 people who receive the injection, 4 to 20 may have:

• Low white blood cell count (cells that fight infections)• Low platelet count (cells that help the blood clot in order to stop bleeding)• Anemia (which may cause tiredness, or may require blood transfusion)• Abnormal liver function test results

Rare, Some May Be Serious In 100 people who receive the injection, 3 or fewer may have:

• Hives, shortness of breath, or an allergic reaction that is life-threatening• Immune reaction to his or her own tissue (autoimmune diseases) or if present, may be made worse.

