6.8.2 Registration/Randomization

6.8.2.1 Fax to [contact] a completed Eligibility Checklist (see CRF packet) to the CPN Registration Office between 8:00 a.m. and 4:30 p.m. Central time, Monday through Friday.

6.8.2.2 Randomization: For details, see Section 13.2.

6.8.2.3 Intervention on this protocol must commence at a CPN institution under the supervision of a CPN clinician.

6.8.2.4 Intervention cannot begin prior to Registration/Randomization and must begin \leq 14 days after Registration/Randomization.

6.8.2.5 Pathology and colonoscopy reports confirming diagnoses must be sent \leq 30 days post Registration/Randomization to the CPN QAS at CPN Operations Office, [name]; or [contact], Attention CPN QAS.

6.8.2.6 Once the intervention assignment has been ascertained by the CPN Registration Office, the appropriate blinded study agent information (MUC1 vaccine or placebo/saline injection) will be communicated to the designated data manager/nurse/pharmacist at the participant's Participating Organization. The name of this contact person is to be entered in the designated space on the eligibility checklist so the Registration Office personnel have it for each participant at the time of registering/randomizing the participant. Make sure this contact person will be available at the time of the registration so he or she can receive the information from the Registration Specialist. This contact person may not be involved in assessing adverse events or any other outcome measure and should not be the same person listed on page one of the eligibility checklist form as the person completing the form. The last page of the eligibility checklist form should provide the source of communication for the contact person, either fax or email, and the appropriate contact information.

6.8.2.7 Stratification Factors:

- Number of advanced adenoma on qualifying colonoscopy: ≥ 3 vs. < 3
- Gender: male vs. female

After the participant has been registered on to the study, values of the stratification factors will be recorded. Randomization will be performed by CPN personnel. The CPN electronic-based randomization system will be utilized to ensure that randomization of participants to appropriate study arms while balancing the stratification variables is carried out successfully.

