13.7 Evaluation of Toxicity (secondary endpoint)

All participants will be evaluable for adverse events (AEs) from the time of their first dose of MUC1 or Placebo during parts 1 and 2 of the study. To evaluate the AE profiles associated with each arm, the maximum grade for each type of adverse event will be recorded for each participant and frequency tables will be reviewed to determine the overall patterns. The number and severity of adverse events

(overall and by arm) will be tabulated and summarized across all grades. Grade 3+ adverse events will be similarly described and summarized separately. As per NCI CTC Version 4.0, toxicities are defined as adverse events that are classified as either possibly, probably, or definitely related to the interventional agent. Overall toxicity incidence, as well as toxicity profiles will be explored and summarized within and across the MUC1 and placebo arms. Frequency distributions, graphical techniques, and other descriptive measures will form the basis of these analyses. In addition, we will review all adverse event data that are graded as 3, 4, or 5 and classified as either "unrelated or unlikely to be related" to the study intervention in the event of an actual relationship developing.

In addition, we will assess patient reported vaccine-related side effects from the Vaccine Report Card as an exploratory analysis. We will summarize the results descriptively and compare the results between the 2 arms.

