13.8 Evaluation of Response

All randomized participants who are evaluated at week 0 and week 12 and have IgG values from those timepoints will be evaluable for the primary endpoint of this study using the intent-to-treat principle. All conclusions regarding efficacy will be based on all participants who completed both week 0 and week 12 and have IgG values from those timepoints as well. Subanalyses may be performed on the subsets of participants, excluding those for whom major protocol deviations have been identified (e.g., early death due to other reasons, early discontinuation of intervention, major protocol violations, etc.). However,

sub-analyses may not serve as the basis for drawing conclusions concerning efficacy, and the reasons for excluding participants from the analysis should be clearly reported. For all measurements of response (i.e. the primary endpoint), the 95% confidence intervals will also be provided.

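### Section 8.4 takes first-dose violators out of a primary analysis set that 13.6 and 13.8 keep them in, and the data cut-off in 8.3 and 8.4 conflicts with the plan's own safety follow-up and adverse event analyses

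*Combined protocol and SAP*

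**What the plan says.** **Off-agent and off-study rules.** Section 8.3 names ineligibility and major treatment violation among the reasons for stopping study agent, and then states: "Participants will continue to be followed, if possible, for safety according to the intended schedule of events (see Section 7". The last sentence of the same section sends these two groups to 8.4 and asks for their data only up to the date on which the status is confirmed. Section 8.4 repeats that limit. For a dosed participant found ineligible it reads: "If participants received study intervention, on-study materials and all data up until the point of confirmation of ineligibility will be submitted". The bullet for a major treatment violation carries the same cut-off, and the definition there says that after a grossly wrong first administration the participant's "data can no longer be used for the primary endpoint". Section 8.4 describes these cases as uncommon.

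**Primary analysis set.** Sections 13.6 and 13.8 include all randomized participants who have IgG values at Week 0 and Week 12, under the intent-to-treat principle. Section 8.1 describes the same set as modified intent-to-treat. Section 13.8 lets participants with major protocol deviations be left out of sub-analyses, but adds that "sub-analyses may not serve as the basis for drawing conclusions concerning efficacy". Section 13.6 rules out imputation. Section 5.7.2 defines evaluability for the primary endpoint differently, by receipt of the Week 0, 2 and 10 injections.

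**Safety and later follow-up.** Section 13.7 says "All participants will be evaluable for adverse events (AEs) from the time of their first dose of MUC1 or" placebo, during Parts 1 and 2. Section 8.2 bases adverse event analyses on all randomized participants. Section 13.1 says that all patients are followed for the Part III adenoma endpoint.

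**The concern.** Two things are at stake.

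The first is who is in the primary analysis. A participant whose first injection was badly wrong but who has both IgG values is in under 13.6 and 13.8 and out under 8.4. The coordinating center assigns the violation status after randomization. The documents do not say that this decision is made blind, and pharmacy staff know the assignment (section 5). Removing randomized participants on such a status is the practice that 13.8 confines to sub-analyses.

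The second is the safety record. A participant who has been injected remains at risk of later events whether or not an eligibility criterion turns out to have been missed. If data after confirmation are not submitted, those events are absent from the 13.7 tables and from the stopping rule in 13.7.1, which covers the first 57 weeks. An early confirmation could also cost the Week 12 IgG value.

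**Working it through.** **1. The definitions applied to specific participants.**

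| Participant | 5.7.2 | 8.1, 13.6, 13.8 | 8.4 |
|---|---|---|---|
| First-dose violator, three injections, both IgG values | in | in | out |
| First-dose violator, stopped before Week 10, both IgG values | out | in | out |
| Dosed, found ineligible, stopped before Week 10, both IgG values | out | in | no exclusion stated, but data after confirmation not required |
| Dosed, found ineligible, no Week 12 value | depends on injections | out (no value) | data after confirmation not required |

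The first three rows give different answers in different sections. The last row does not conflict with 13.6: without a Week 12 value there is no ratio. The two descriptions of a major treatment violation also differ. Section 8.3 ties it to the first week after randomization, and 8.4 ties it to the first administration, which 6.8.2.4 allows up to 14 days after randomization.

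**2. Timing.** From the visit windows in section 7.1:

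- Week 2 injection: at least 14 days after Week 0.
- Week 10 injection: at least 7 weeks (49 days) after Week 2.
- Week 12 sample: at least 10 days after Week 10.

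The earliest in-window Week 12 sample is therefore 14 + 49 + 10 = 73 days after Week 0. Section 6.8.2.5 says "Pathology and colonoscopy reports confirming diagnoses must be sent" within 30 days of randomization. The Week 0 injection falls 0–14 days after randomization and the Week 2 injection 14–28 days after that, so 14–42 days after randomization. When reports arrive, a participant may have had none, one or two injections. If ineligibility is then confirmed before Week 12, the primary IgG value falls after the cut-off.

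**3. Stopping rule.** Section 13.7.1 acts by arm when 20% of participants have a related grade 3 or higher event. With 55 treated in an arm, 11/55 = 20.0% meets the threshold. If one of those 11 events came after a cut-off and was not submitted while the participant stayed in the denominator, the count would be 10/55 = 18.2% and the rule would not act. The documents do not say how such participants are counted.

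**4. Size on the primary endpoint.** Inputs from 13.4: mean ratio 6.5 against 1 (difference 5.5), SD 10, 50 evaluable per arm, one-sided alpha 0.05.

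- Non-centrality = 5.5 / (10 × √(2/50)) = 2.75, with 98 degrees of freedom.
- Power by the noncentral t distribution = 86.1%; by normal approximation 86.5%. The plan states at least 86%, so its figure is reproduced.

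The number affected per arm, k, is not in the documents; 1 to 5 is an assumption. Excluding k per arm uses n = 50 − k. Keeping them, with no response at all in the k vaccine participants (worst case), uses n = 50 and a difference of 5.5 × (1 − k/50), with the SD left at 10.

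| k per arm (assumed) | Excluded | Kept, worst case |
|---|---|---|
| 1 | 85.5% | 84.9% |
| 2 | 84.9% | 83.6% |
| 3 | 84.2% | 82.2% |
| 4 | 83.5% | 80.7% |
| 5 | 82.7% | 79.2% |

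**The case against.** The case on the other side is substantial, and it limits the point in several ways.

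- **Submission, not collection.** A reader might infer that sites stop collecting data on injected participants. Section 8.4 does not say so. The words "No further data submission is necessary. No follow-up is required" are written for undosed ineligible participants and for cancels, not for the dosed groups. This stands. But 8.4 introduces its bullets as covering both data submission and follow-up, so a site could take the cut-off as final. Even on the narrow reading, later data do not reach the analysis.
- **Not an all-randomized primary analysis.** Sections 13.6 and 13.8 require both IgG values, so an ineligible participant without a Week 12 sample is simply non-evaluable. This stands, and it confines the direct conflict to participants who have both values.
- **Thirty days is a deadline for reports.** A reader might infer that everyone found ineligible at this check has been injected and never reaches Week 12. No date is set for confirmation, and eligibility is also checked at pre-registration, by local report review and by the registration checklist. Loss of the Week 12 value is possible, not certain.
- **Autoimmune risk.** Section 6.2 lists as a rare risk "Immune reaction to his or her own tissue (autoimmune diseases) or if present, may be made worse", and it is tempting to say that the people cut off are the ones most exposed to it. The 30-day check covers endoscopy and pathology reports, not autoimmune history, and ANA is screened before randomization. Section 11.1.1 requires all adverse events to be recorded, 11.1.5 requires clinically significant ones to be followed, and 11.2.3 has serious events that are at least possibly related followed until resolved. What the cut-off leaves in doubt is whether later non-serious events and the Week 52 ANA are submitted.
- **Imbalance between arms.** The active injection is admixed and placebo is plain saline, so one might expect first-dose errors mainly in the vaccine arm. No data support this, and dispensing the wrong product could affect either arm.
- **Retention can cost more power than exclusion.** In the worst case at five per arm, keeping gives 79.2% and excluding 82.7%. This is correct, but it assumes no response in any retained vaccine participant, and 13.8 already chooses retention for the analysis that supports conclusions.

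**Conclusion.** Two conflicts are established from the text. First, 8.4 bars a first-dose violator's data from the primary endpoint, while 13.6 and 13.8 include that participant if both IgG values exist, and 5.7.2 applies a third rule. Second, the cut-off in 8.3 and 8.4 is inconsistent with 8.3's own follow-up sentence and with the adverse event populations in 8.2 and 13.7.

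The numerical effect on the primary test is small if cases are as uncommon as 8.4 says: 0.6 to 3.4 percentage points of power for 1 to 5 exclusions per arm, a range that is assumed. The importance lies in a post-randomization exclusion from the primary set and in an incomplete safety record for people who were injected. The documents do not support saying that follow-up is ended, that every ineligible participant loses Week 12, or that exclusions fall on one arm. The wording should be corrected.

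**What to change.** Reconcile 5.7.2, 8.1, 8.3, 8.4 and 13.6–13.8. For any randomized participant who has received at least one injection:

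- State that neither ineligibility nor major treatment violation ends submission of scheduled adverse event and laboratory data, the Week 12 IgG sample, or colonoscopy reports. Amend the last sentence of 8.3 and the 8.4 bullets to match.
- Analyse available Week 0 and Week 12 IgG values in the assigned arm. Delete the clause in 8.4 that bars use for the primary endpoint, and keep such exclusions for the 13.8 sub-analyses.
- Use one name and one definition for the primary set in 8.1, 13.6 and 13.8, and bring 5.7.2 into line with it.
- Use one definition of major treatment violation in 8.3 and 8.4.

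Whether further injections are given is a separate clinical matter and is not addressed here.

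The cost is a wording change plus visits already on the schedule for what should be few participants. The downside is some dilution: power of 84.9% to 79.2% if 1 to 5 per arm (assumed) are kept and those in the vaccine arm do not respond at all.
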